8.2.6 HeadOn symptom diary data

As part of our analysis, we aim to examine the association between data collected in the HeadOn symptom diary and functional outcome. Participants will be dichotomised based on their aggregate scores of the symptom diary. Logistic regression will then be used to examine its predictive relationship with GOSE outcome.

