3 STUDY DESIGN

The HeadOn feasibility study is a prospective feasibility study of patients presenting to the Edinburgh Royal Infirmary and St John's Hospital Emergency Departments (ED) (**Figure 1**). Patients will be identified from the ED. Potentially eligible patients will be contacted by a member of the Emergency Medicine Research Group Edinburgh (EMERGE) research team and their consent will be sought for participation. Those not recruited at presentation to the ED will be contacted by telephone, text or email within two weeks of their concussion date to seek their participation in the study, again by a member of the EMERGE research team. After consenting, the participant will be taken through the registration process for the HeadOn program. For patients who are contacted after discharge they will be taken through registration process over the telephone or if preferable will be able to return to the ED to go over the process.

At registration the participant will be invited to complete a series of patient reported measures including the Rivermead post-concussion questionnaire, Pittsburgh Sleep Quality Index, PHQ9 questionnaire and FAST alcohol questionnaire within the HeadOn program. Alongside this, a series of researcher-led anonymised data points will be collected in a separate specially designed database including demographics, date of concussion, neurological and imaging findings which will all be collected from the medical notes and imaging reports. The HeadOn program runs for five weeks following which the participant will be invited to complete the same set of outcome measures. Alongside this, all the participant will be contacted (via telephone, text or email) by a member of the research team at week 5 to complete a further five measurements: Glasgow Outcome Score Extended, mHealth App Usability questionnaire, time to return to work and a healthcare utility questionnaire. Interested participants will be invited back within two months of enrolling in the study for a more detailed qualitative interviews about HeadOn. The study will recruit for a period of 6-months or up to 100 participants.

[figure not shown]

Figure 1: Schematic of HeadOn study design

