4.2 INCLUSION CRITERIA

- Patients aged 16 years and older (no upper age limit)
- Presenting to the ED with a concussion
- Concussion defined as a traumatically induced alteration of mental status (either defined as loss of consciousness and/or amnesia)
- Patient is Glasgow Coma Scale score of 13-15 on initial presentation to the ED
- Patient needs to be able to start using HeadOn within 14 days of their head injury

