6. DATA COLLECTION

Data will be collected at four points during the study period: at baseline, during the HeadOn program, at the final 5-week follow-up and during a voluntary qualitative interview. Two forms of data will be collected: patient-reported and researcher collected.

At baseline, participants will complete four patient questionnaires within the HeadOn program (Rivermead postconcussion, PHQ9, Pittsburgh Sleep Quality and the FAST alcohol screen). Researchers will also capture demographic, clinical and imaging findings data taken from participants notes and investigation finding reports. During the HeadOn program, participants will undergo a series of ecological momentary assessments (EMAs) aimed at capturing information about their symptoms, mood, thoughts about their concussion and behaviour (**Appendix**). This includes a symptom and mood diary which will be delivered daily. Alongside this, a series of other EMAs are delivered to the participant at different stages of the program (**Figure 2**): Stage 3 (Alcohol tracker), Stage 4 (Thought diary) and Stage 5 (Goal setting). HeadOn generates automated reminders (by email or notification) to help keep participants engaged. In the final 5-week follow-up of the study, both participant-reported and researcher collected outcome measures will be captured. Participants will complete the following questionnaires digitally through the HeadOn program: Rivermead postconcussion, PHQ9, Pittsburgh Sleep Quality and FAST alcohol screen. The participant will also be contacted by a trained member of the HeadOn research team to complete four questionnaires: the mHealth app usability questionnaire, healthcare utility, return to work questionnaire and the Glasgow Outcome Score Extended (GOSE). The participant will also be reminded to complete the week 5 patient-reported questionnaires if they had not already done so. If the participant has not completed these questionnaires by week 6, then they will be contacted again by a member of the research team to complete these questionnaires.

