8.2.3 Patient compliance

During each stage of the program participants are required to input data as part of the CBT tasks. Participants will be divided into the following three groups:

- a) *Fully compliant*: participants who input data into the program during all five stages
- b) *Partially compliant*: participants who input data but not during all five stages
- c) *Non-compliant*: participants who do not enter any data into the program

We plan to conduct simple descriptive analysis to better understand trends in patient interaction with HeadOn.

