8.2.5 Functional outcome

The Glasgow Outcome Scale extended is being used to determine functional outcome in this study. It is an 8-level scale with 8 representing a complete recovery down to 1 which is death. We plan on dichotomising participants to complete recovery (score 8) versus incomplete recovery (<8). Logistic regression will then be used to examine the predictive role of a range of admission data points (demographics, clinical findings (LOC vs no LOC, amnesia vs no amnesia) and admission patient reported measures (Rivermead, PHQ9).

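### Section 8.2.6 splits the symptom-diary score in two at an unstated cut before logistic regression on GOSE, which discards information, and sets no diary window to support the word 'predictive'

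*Combined protocol and SAP*

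**What the plan says.** Section 8.2.6 opens by stating its aim: "we aim to examine the association between data collected in the HeadOn symptom diary and functional outcome". It then gives the method: "Participants will be dichotomised based on their aggregate scores of the symptom diary". It ends: "Logistic regression will then be used to examine its predictive relationship with GOSE outcome".

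No cut, and no rule for choosing one, appears anywhere in the document. The section also does not say whether the aggregate is a sum or a mean, which days it covers, or how missed days count. The diary in Appendix VIII has eight items, each running from none to severe.

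The neighbouring Section 8.2.5 is more specific. It states its GOSE cut (8 versus below 8) and describes no split of the baseline Rivermead or PHQ9 scores. There the predictive wording is attached to baseline data: "Logistic regression will then be used to examine the predictive role of a range of admission data points".

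On timing, Section 6 says of the assessments made during the program: "This includes a symptom and mood diary which will be delivered daily". Section 3 gives the program five weeks and has participants contacted "by a member of the research team at week 5 to complete a further five measurements: Glasgow Outcome Score Extended".

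**The concern.** Three things are left open or lost.

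- **Information.** A score built from eight items over many days is reduced to high or low. The odds ratio will be less precise than the same data allow.
- **The cut.** Because none is stated, it could be settled after the diary and GOSE data have been seen. A nominal p-value would then not carry its usual meaning.
- **The window.** With no start or end day set, the aggregate may include entries made just before, or even after, the GOSE contact. Those entries describe much the same state that GOSE rates. Calling the result predictive could lead a reader to think that early diary data foretell recovery, when late entries may be driving the link.

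What is at stake is one exploratory result that might inform later trials. The compliance and usability endpoints do not depend on it.

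**Working it through.** **Inputs from the plan.** The recruitment target is 100 (Sections 3, 4.1 and 8.1). The outcome is GOSE below 8 versus 8 (Section 8.2.5). Section 8.2.6 has no cut, effect size, significance level or power of its own to reproduce. The only sample-size arithmetic is in Section 8.1: 500 × 0.30 = 150, whereas 100/500 = 20%. The 100 can be read as a cap, since Section 3 recruits up to that number. That mismatch is a separate matter; n = 100 is used here.

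**Inputs assumed.** The documents give no diary or GOSE figures. The shape of the score, the odds ratio per SD and the proportion with incomplete recovery are therefore assumptions.

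**1. Information kept.** For a weak association, the fraction kept by a split is the squared correlation between the score X (mean 0, SD 1) and the indicator X > c. That is {E[X·1(X > c)]}² / {q(1 − q)}, where q is the proportion below the cut.

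- Normal score, where the expectation is φ(z_q):
  - median: 0.3989² / 0.25 = 0.637
  - 25th or 75th percentile: 0.3178² / 0.1875 = 0.539
  - 20th or 80th percentile: 0.2800² / 0.16 = 0.490
- Exponential score (a skewed example), where the expectation is c·e^(−c):
  - median, c = ln 2: (0.693 × 0.5)² / 0.25 = 0.48
  - 80th percentile, c = ln 5: (1.609 × 0.2)² / 0.16 = 0.65

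So 100 participants with a median-split normal score carry the information of about 64 with the continuous score. Under skewness the figures move and the best cut is no longer the median, but every split still loses something.

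**2. Illustrative power at n = 100.** The main simulation used 10,000 studies per scenario, a normal severity, day-to-day diary noise averaged over 35 completed days, and a Wald test at 1.96. With an odds ratio of 2 per SD and 50% incomplete recovery:

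| Score entered as | Power |
|---|---|
| Continuous | 0.886 |
| Median split | 0.743 |
| Split at 25th / 75th percentile | 0.618 / 0.621 |

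A separate simulation without diary noise, using a likelihood-ratio test and 3,000 studies, gave 0.900 continuous and 0.752 split at the median. Over odds ratios 1.5 to 2.5 and incomplete recovery of 30% to 70%, the median split costs between 0.984 − 0.918 = 0.066 and 0.832 − 0.629 = 0.203, or about 7 to 20 percentage points.

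**3. Effect of an open cut.** With no true association (n = 100 and 70, incomplete recovery 30% to 70%), one fixed median cut gave p < 0.05 in 4.7% to 5.6% of studies. Reporting the best of the 25th, 50th and 75th percentile cuts gave 12.2% to 13.7%.

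**4. Timing.** The diary runs daily through a five-week program and GOSE is taken at the week-5 contact, so most entries should precede the outcome. Nothing closes the diary at that contact, however. Section 12.6 restricts access only once the study is completed, and the home-page screenshot in Appendix VII shows a user on day 125 with the diary still listed as a task. The screenshot may be only illustrative.

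**5. Why a mean over all completed days is not enough.** Section 8.2.3 provides for "participants who input data but not during all five stages", so length of use may differ. Suppose, as an assumption, that everyone's daily total falls linearly from 20 on day 1 to 4 on day 35, a drop of 16/34 = 0.471 per day. Someone who stops after day 7 has a mean of 20 − 3 × 0.471 = 18.6; a full completer has (20 + 4)/2 = 12.0. The trajectories are identical but the scores differ. A window common to all participants largely removes this.

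**The case against.** Section 8.2.6 is one exploratory analysis in an uncontrolled feasibility study. The diary–GOSE association is not among the endpoints in Section 2.2, and the plan sets no significance level or power for it, so power figures have limited weight. Two groups are easy to present. All of this stands, and it is why the point is rated low. It does not make the split harmless, since the same data can be used without it.

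Three stronger readings are tempting, and the documents do not support them:

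- **That diary and GOSE are concurrent, so 'predictive' is wrong.** Sections 3 and 6 place most diary entries before the week-5 contact. The gap is the missing window. The section's own first sentence already speaks of an association.
- **That the plan has an inflated false-positive rate.** The 12–14% applies only if the analyst tries several cuts and reports the best. Section 8.2.6 does not say that; it merely does not rule it out.
- **That 64% is a firm figure and the median the best available cut.** Both depend on a roughly normal score. The exponential example gives 48% at the median and 65% at the 80th percentile.

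**Conclusion.** The point holds in limited form. Splitting the diary score loses information whatever its shape: about 36% at a median split and 46% at a quartile cut if the score is roughly normal and the association weak. The power comparison of 74% with 89% is an illustration that rests on an assumed odds ratio of 2 per SD, 50% incomplete recovery, a normal score and 100 participants with full diaries. The unstated cut leaves room for a data-driven choice, without any sign that one is intended. The missing window means that late entries may overlap the outcome, so 'association' is the safer description unless the score is limited to early entries. The compliance and usability endpoints are unaffected. This is a change the sponsor could make, not one the study depends on.

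**What to change.** Replace the last two sentences of Section 8.2.6 with:

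> The diary score is the mean daily item total over completed diary days within one fixed early window common to all participants (for example stage 1), ending before the GOSE contact. It is entered as a continuous variable (per SD) in a logistic regression of GOSE (<8 v 8) and reported as an association. Participants with no entry in the window are reported as missing, and the number of completed days is reported. Any grouping of the score is for descriptive display only.

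The mean over all completed days before GOSE may be added as a sensitivity analysis, with a note that it depends on when a participant stopped using the diary.

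No new data are needed, provided that diary entries and the GOSE contact are dated. The costs are these:

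- The simple two-group presentation is lost, though a table of GOSE below 8 by quarter of the score can replace it.
- Linearity in the log-odds is assumed.
- Later diary entries drop out of the main model.
- An early window does not fall at the same time after injury for everyone, because Section 4.2 asks only this: "Patient needs to be able to start using HeadOn within 14 days of their head injury". The date of concussion is already collected (Section 3), so the interval can be reported.
- Section 8 is part of the protocol, so the change needs an amendment under Section 12.1. Given the low priority, it is best combined with other amendments.

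### Section 8.2.6 names only the symptom-diary score as a predictor of GOSE, so it cannot show whether the diary tells more than the baseline Rivermead score

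*Combined protocol and SAP*

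**What the plan says.** Section 8.2.6 defines the predictor: "Participants will be dichotomised based on their aggregate scores of the symptom diary". It gives no cut-point. The analysis sentence is: "Logistic regression will then be used to examine its predictive relationship with GOSE outcome". No covariate is named, and the text does not say whether the model is crude or adjusted.

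The outcome comes from Section 8.2.5, which plans on "dichotomising participants to complete recovery (score 8) versus incomplete recovery (<8"). That section has its own logistic model, whose candidate predictors include "admission patient reported measures (Rivermead, PHQ9"). Nothing links the two models.

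The timing is set out in Sections 6 and 3:

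- Baseline: "At baseline, participants will complete four patient questionnaires within the HeadOn program (Rivermead postconcussion, PHQ9, Pittsburgh Sleep Quality and the FAST alcohol screen").
- During the program: "This includes a symptom and mood diary which will be delivered daily".
- Outcome: participants are contacted "by a member of the research team at week 5 to complete a further five measurements: Glasgow Outcome Score Extended" and others.

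**The concern.** Baseline severity comes before both the diary and GOSE, and the diary asks about the same symptoms as the baseline form. A participant with many symptoms at registration is likely to score high in the diary, and may also be less likely to reach GOSE 8. The plan itself treats baseline Rivermead as a candidate predictor of GOSE in 8.2.5. An association between diary and GOSE can therefore arise through initial severity alone, even if five weeks of daily entries add nothing to the one form completed at the start.

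No planned model contains both measures, so the analysis cannot separate a diary that carries new information from one that re-measures baseline severity. What is at stake is the interpretation: a crude result described as predictive could be taken to mean that the diary adds prognostic information, which this model cannot establish.

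**Working it through.** **Overlap of content.** The eight items of the diary (Appendix VIII) against the 16 items of the Rivermead questionnaire (Appendix I):

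| Diary | Rivermead counterpart |
|---|---|
| Headache | Headaches |
| Dizziness | Dizziness |
| Sleep disturbance | Sleep disturbance |
| Fatigue | Fatigue |
| Irritability | Irritability |
| Low mood | Depressed or tearful |
| Poor memory | Forgetfulness |
| Difficulty concentrating | Poor concentration |

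All 8 of 8 diary items are matched.

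**Inputs.** The plan states no significance level, power, effect size or expected GOSE rate for 8.2.6, so there is no figure of its own to reproduce. The only number taken from the documents is the recruitment target of 100 (Sections 4.1 and 8.1). Everything else is assumed: diary-severity correlation ρ of 0.5-0.8, odds ratio (OR) for incomplete recovery of 1.5-3 per SD of initial severity, 30-50% with GOSE below 8, a median split of the diary, and a two-sided 5% test.

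**Model.** Let S be initial severity (standard normal).

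- Diary: D = ρS + √(1 − ρ²)·e, with no effect of its own on GOSE. The diary group d is 1 if D is above its median.
- Outcome: logit P(GOSE < 8) = a + ln(OR)·S.
- Crude model: GOSE on d. Adjusted model: GOSE on d and the baseline score B.
- B = S if baseline is error-free; otherwise B = √r·S + √(1 − r)·e′ with reliability r.

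**Check by hand.** A median split on D separates the two groups' mean severity by 2ρ√(2/π) = 1.596ρ SD. The expected crude odds ratio is then roughly exp(1.596ρ·ln OR).

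- ρ = 0.5, OR 1.5: exp(0.798 × 0.405) = exp(0.323) = 1.38.
- ρ = 0.7, OR 2: exp(1.117 × 0.693) = exp(0.774) = 2.17.

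The simulated medians are 1.36-1.38 and 2.06-2.08. Some shrinkage is expected, because severity also varies within each group.

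**Simulation, N = 100, error-free baseline, 1,500 runs per setting (selected rows).** Entries are the share of runs with p < 0.05 for the diary term, with the median odds ratio in brackets.

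| GOSE < 8 | ρ | OR per SD | Crude | Adjusted |
|---|---|---|---|---|
| 30% | 0 | 2 | 5.4% (1.00) | 5.1% (1.01) |
| 30% | 0.5 | 1.5 | 10.1% (1.36) | 4.9% (0.99) |
| 30% | 0.7 | 2 | 35.8% (2.06) | 5.0% (0.97) |
| 30% | 0.7 | 3 | 66.1% (2.95) | 5.3% (1.01) |
| 50% | 0 | 2 | 5.9% (1.00) | 5.6% (1.03) |
| 50% | 0.5 | 1.5 | 12.4% (1.38) | 4.7% (1.02) |
| 50% | 0.7 | 2 | 45.3% (2.08) | 4.5% (1.01) |
| 50% | 0.7 | 3 | 73.5% (2.90) | 5.1% (0.98) |

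For ρ of 0.5-0.7, the crude rate runs from 10% to 74% and the adjusted rate from 4.5% to 6.3%. With ρ = 0 the crude rate is near 5%, so the excess comes from initial severity. Runs that extend ρ to 0.8 (800 per setting) take the crude rate to 85% and the median odds ratio to 3.5, with adjusted rates of 4-7%.

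**Fewer usable participants.** With N = 60 and ρ of 0.5-0.7, the crude rate is 9-51% and the adjusted rate 4.1-7.0%.

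**Baseline measured with error (r = 0.8, N = 100, 50% with GOSE < 8).**

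| ρ | OR per SD | Crude | Adjusted |
|---|---|---|---|
| 0.5 | 2 | 24.9% (1.63) | 7.1% (1.14) |
| 0.5 | 3 | 44.1% (2.07) | 7.1% (1.18) |
| 0.7 | 2 | 43.7% (2.07) | 7.5% (1.19) |
| 0.7 | 3 | 72.6% (2.74) | 9.9% (1.36) |

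Adjustment removes most of the severity effect, but not all of it.

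**The case against.** The strongest reply is that 8.2.6 sets out only to look at association. It makes no claim of independent or added value, and a predictor need not be independent of baseline to predict. That stands: the crude model is a legitimate description, and it should stay.

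Four stronger readings are tempting, and the documents do not support them.

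- A reader might take the 10-85% as a false-positive rate. It is not. In the simulation the diary truly is associated with GOSE, through severity, so these rates are power to detect a real marginal association. They would mislead only if the result were presented as added value.
- A reader might infer that the result will decide whether a daily diary is kept in the next trial. No section says so. Data entered for the program's tasks define compliance (2.2.1), the symptom diary is one of those tasks (1.2), and what Section 1.2 names as guiding future trials is recruitment rates.
- A reader might infer that the plan specifies an unadjusted model. It is silent. Naming only the diary makes a single predictor the natural reading, but one sentence would settle it.
- A reader might infer that adjustment makes any remaining diary effect predictive. The diary runs daily and GOSE is taken at week 5, so late entries are nearly concurrent with the outcome. They could add to baseline for that reason alone, and the simulation excludes this by construction.

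It is also fair to say that setting a dichotomised diary against a continuous Rivermead score would handicap the diary.

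**Conclusion.** The point holds as a limit on what 8.2.6 can show. With the diary as the only named predictor, the analysis describes a crude association and cannot say whether the diary adds to a baseline form that covers all eight of its items.

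Only the direction is firm. The size rests on the assumed correlation, odds ratio, recovery rate and median split, none of which the documents give, and on all 100 participants supplying both diary and GOSE data. Section 8.2.3 allows for participants who enter nothing. The adjusted rate of about 4-7% also needs an error-free baseline score; at reliability 0.8 it is 7-10%. The simulation kept the median split throughout and does not cover a continuous diary score.

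The analysis is exploratory. It is not among the endpoints in Section 2.2 and does not touch the primary endpoints of compliance and usability.

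**What to change.** In 8.2.6:

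- Keep the crude diary-GOSE estimate and label it as crude.
- Add a logistic model of GOSE on baseline Rivermead (continuous), then add the diary score, also continuous so that the comparison is fair. Fit both steps on the same participants.
- Report the adjusted diary odds ratio with its confidence interval and the change in model fit. Claim added predictive value only from this model.
- State that diary entries close to week 5 are nearly concurrent with GOSE, so an adjusted association is not by itself evidence of early prediction.
- Report how many participants are left out for having no diary data.

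The cost is a few sentences, one covariate already collected and one more parameter. The diary odds ratio will probably be smaller and less precise. With an assumed 30-50 incomplete recoveries in 100 participants, two model terms are supportable.
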